#### **3.2. Study Duration and Follow-up**

After FDA and institutional review board (IRB) approval of the protocol, enrollment of individuals in the surveillance program and data collection will commence. The study is planned to end no earlier than April 2035, with 10 years of data collection. Interim reports will be prepared annually, and a final report will be submitted upon completion. However, the study may be extended based on the achieved enrollment and follow-up of patients.

For each prospectively enrolled individual, participation will begin at enrollment (during pregnancy) and end at pregnancy outcome (if fetal loss) or 1 year after pregnancy outcome (if live birth).

For each retrospectively enrolled individual, participation will begin after the pregnancy outcome has occurred and all available pregnancy data will be collected at enrollment. Individuals exposed during lactation only will be reported separately from pregnancy exposure cases.

## **4. STUDY POPULATION**

### **4.1. Participant Enrollment**

To maximize participation and capture as many pregnancy and/or lactation exposures as possible, the surveillance program will allow multiple means of enrollment.

Enrollment in the surveillance program may be accomplished, as follows:

- Eligible pregnant or lactating individuals may self-enroll or be enrolled by their HCPs by providing informed consent and medical release(s) to the virtual research coordination center (VRCC; see Section 11.4.3).
- Where applicable, HCPs may enroll pregnant or lactating individuals under an IRB-/ethics committee (EC)-approved waiver of informed consent and provide de-identified data to the VRCC.

Pregnant or lactating individuals who are interested in participating may self-enroll in the surveillance program by calling the VRCC. To enroll, individuals will answer a series of screening questions designed to assess their eligibility and, if eligible, they will provide informed consent, their primary contact information, alternate contact information for a family member or friend outside of the household, contact information for HCPs who are/will be involved in their care or the care of their infants, and medical releases to allow these HCPs to provide data to the surveillance program.

HCPs may enroll pregnant or lactating individuals who they have identified in their practices and who meet eligibility criteria in the surveillance program with informed consent or under an IRB-/EC-approved waiver of informed consent. If the participant is enrolled under an IRB-/EC-approved waiver of informed consent, only de-identified data will be collected from the HCP. HCPs may refer individuals interested in self-enrolling to the VRCC or obtain consent and medical release(s) from the individuals directly. If an individual refuses to provide consent, no data (not even de-identified data) will be collected.

The surveillance program may collaborate with the existing registries/studies to identify individuals who have been exposed to omaveloxolone during pregnancy or lactation. The patients identified via existing registries/studies will be able to enroll in the surveillance program via the methods described above, based on their geographic location.

### **4.2. Study Population Enrollment Criteria**

The study population will include individuals of any age who are exposed to at least 1 dose of omaveloxolone at any time during pregnancy and/or lactation.

#### **4.2.1. Inclusion Criteria**

Each individual must meet the following inclusion criteria to be eligible for this study:

- Exposure to at least 1 dose of omaveloxolone per label for FA at any time during pregnancy (from 12 days prior to conception to pregnancy outcome) and/or at any time during lactation (up to 1 year of infant age or weaning, whichever comes first).

- Informed consent or IRB-/EC-approved waiver of informed consent.

#### **4.2.2. Exclusion Criteria**

No exclusion criteria are defined.

#### **4.2.3. Enrollment Criteria**

The minimum criteria required for enrollment into the surveillance program are:

- Sufficient evidence to confirm that the individual is exposed to at least 1 dose of omaveloxolone per label for FA at any time during pregnancy or lactation
- Sufficient information to determine whether the participant is prospectively or retrospectively enrolled (i.e., whether the outcome of pregnancy occurred prior to first contact with the surveillance program)
- Full contact information for the reporter who enrolls the participant (i.e., pregnant or lactating individual, or HCP) to allow for follow-up

Participants without the minimum criteria for enrollment will be considered invalid and will not be included in the analysis population.

## 5. PARTICIPANT RECRUITMENT AND RETENTION

### 5.1. Recruitment Strategy

A targeted, multi-pronged recruitment campaign may be employed to recruit participants for the surveillance program. The campaign may target individuals who are pregnant or lactating, individuals using omaveloxolone, obstetric or pediatric HCPs, HCPs who are likely to treat FA, and HCPs who are likely to prescribe omaveloxolone. HCPs who are known to prescribe omaveloxolone may be identified using the Sponsor's distribution data or by medical science liaisons (MSLs). Obstetric HCPs and HCPs who are likely to treat FA may be identified using HCP directories and/or professional associations. Individuals who are pregnant or lactating and individuals using omaveloxolone may be identified using patient support groups and external data sources, such as pharmacy/medical claims or electronic medical records.

A multi-modal approach may be used to deliver surveillance program education and recruitment materials to targeted HCPs and patients. This approach involves direct-to-HCP outreach as well as online and print advertising directed to HCPs and patients. In addition, stakeholders who contact the Sponsor call center and may be eligible for participation will be referred to the VRCC.

Direct-to-HCP outreach may be achieved by delivering recruitment materials to targeted HCPs via e-mail, fax, and/or hardcopy mail. In addition, MSLs may provide surveillance program education and recruitment materials to HCPs in person. HCPs may be asked to identify potential surveillance program participants and encourage their participation by speaking to them about the surveillance program and providing them with the patient-directed surveillance program recruitment materials.

Information regarding the surveillance program may also be available on the following websites: PPD website (<https://www.ppd.com/our-solutions/clinical/peri-and-post-approval/non-interventional-studies/pregnancy-and-lactation-studies/>), the Sponsor's corporate website (<https://www.biogen.com/>), the FDA listing of pregnancy registries on [www.fda.gov](http://www.fda.gov), [www.clinicaltrials.gov](http://www.clinicaltrials.gov), Society for Maternal-Fetal Medicine listing of registries (available to members via log-in), and the European Network of Centers for Pharmacoepidemiology and Pharmacovigilance website (<http://www.encepp.eu/>). As deemed necessary, online advertisements on social media sites or other relevant websites (e.g., professional association websites or websites commonly visited by individuals who are pregnant or lactating) may be used to direct potential participants to the surveillance program.

Various print materials may also be used to provide information related to the surveillance program and facilitate recruitment. The SKYCLARYS product label and patient package insert will provide surveillance program information, including the surveillance program contact information. Information related to the surveillance program may also be directed to HCPs via announcements/publications in relevant professional journals/newsletters or presentations/exhibits at relevant professional meetings. As deemed necessary, print advertisements in newspapers or magazines with targeted patients among their readership may be used to direct potential participants to the surveillance program, and recruitment materials may be distributed to locations commonly frequented by targeted patients (e.g., ultrasound clinics, clinics that specialize in FA).

The success of the recruitment strategy will be monitored on an ongoing basis. Should additional efforts be required due to lower than anticipated enrollment, changes to the recruitment strategy will be considered at each interim report.

## **5.2. Retention Strategy**

Retention will be facilitated by engaging surveillance program participants in the reporting process and minimizing the burden on reporters. Materials provided will emphasize the mission of the surveillance program to promote engagement and point readers toward the contact information for the program.

The VRCC will serve as the sole point of communication for participants and HCPs. The specialized staff, many of whom are obstetric nurses, have experience collecting data for observational studies from patients and research-naïve HCPs. They are experts at developing a rapport with HCPs and participants to facilitate data collection and build one-on-one relationships that will promote retention and reduce overall loss to follow-up.

The surveillance program will use streamlined data collection processes and simple, concise data collection forms that focus on endpoints of interest to reduce the burden of reporting. The surveillance program will provide multiple options for communication and data submission (e.g., phone, fax, mail, e-mail) and a flexible follow-up schedule to enhance retention and maximize data reporting. The surveillance program will also attempt to collect contact information of family members or friends outside of the household in case the participant cannot be reached, which can further promote retention.

To promote HCP engagement, study results may be shared with HCPs through various means (e.g., e-mail, newsletters).

## 6. DATA COLLECTION

### 6.1. Data Collection Process

Enrolled individuals and the HCPs involved in their care or the care of their infants, if applicable, will serve as data reporters to the surveillance program. If the participant is enrolled by an HCP under an IRB-/EC-approved waiver of informed consent, the HCP who enrolled the participant will be responsible for providing all follow-up data to the surveillance program. It is anticipated that most obstetric data will be collected (directly or via the reporter who enrolled the participant) from the participant's obstetric HCP, defined as any HCP who provides care during pregnancy (e.g., obstetrician, family practitioner, general practitioner); it is anticipated that most pediatric and lactation data will be collected (directly or via the reporter who enrolled the participant) from the infant's pediatric HCP, defined as any HCP who provides pediatric care (e.g., pediatrician, family practitioner, general practitioner). The surveillance program may also request data from other HCPs involved in the individual's or infant's care (e.g., prescriber, specialist) after appropriate medical release is obtained from the individual.

The data collection process for each participant enrolled prior to pregnancy outcome will begin at enrollment, and cumulative data throughout the pregnancy will be collected: at enrollment, at the end of the second trimester (approximately 26 gestational weeks), at pregnancy outcome (live birth or fetal loss), and during lactation. For participants enrolled after pregnancy outcome, all available pregnancy data will be collected at enrollment. For live-born infants, data will be collected at 2 timepoints: approximately 4 months and 1 year after delivery. Data collection forms are described below and will be identical for all enrolled participants regardless of their method of enrollment. Reporters to the surveillance program will use the data collection forms and will be instructed to transcribe data that are readily available in the patients' medical records into the data collection forms. If data are collected via telephone by the VRCC, the VRCC will complete the data collection forms.

Data collected at enrollment will be registration information (including eligibility criteria), maternal demographic characteristics, maternal pre-pregnancy anthropometrics, maternal obstetrical history, family history of congenital malformations, disease information, pregnancy information, and maternal exposures during pregnancy. These data will be collected on the **Registration Form** and **Pregnancy Information Form**. Additionally, see Section 12.3.4 for reporting pregnancies on the **Clinical Trial Pregnancy Notification and Outcome Form**. At approximately the end of the second trimester, the appropriate reporter will be asked to complete another **Pregnancy Information Form**, which will collect any updates to pregnancy information and maternal exposures during pregnancy. Around or after the estimated date of delivery (EDD) or after a known pregnancy outcome, the appropriate reporter will be asked to complete another **Pregnancy Information Form** as well as the **Pregnancy Outcome Form**, which will collect pregnancy outcome information (including gestational age at outcome) as well as any updates to pregnancy information and maternal exposures during pregnancy. Additionally, see Section 12.3.4 for reporting the outcome of pregnancies on the **Clinical Trial Pregnancy Notification and Outcome Form**.

For each live-born infant, the appropriate reporter will be asked to complete an **Infant Outcomes Form** and **Maternal Lactation Information Form**, which will collect infant information, including breastfeeding information, infant growth and development data, and maternal lactation

outcomes at 2 timepoints: approximately 4 months after delivery and approximately 1 year after delivery.

Data related to congenital malformations will be solicited at all data collection timepoints (at enrollment and throughout pregnancy on the **Pregnancy Information Form**, which collects data on prenatal testing, at pregnancy outcome on the **Pregnancy Outcome Form**, and throughout the infant’s first year of life on the **Infant Outcomes Form**). If a congenital malformation (major or minor) or other event of interest is reported, additional information may be requested from the reporter on the **Targeted Follow-up Form** to properly characterize the event. Outcomes of pregnancies that meet serious adverse event (SAE) reporting requirements are included in Section 12.3.2. The date each data collection form is completed will also be collected. Table 1 provides a summary of the data collection process, including the forms that will be used to collect the data, the timing of the completion of each form, the potential reporters or sources of the data, and the types of data that will be collected. Section 6.1.1 provides further details regarding the data collected.

**Table 1. Summary of Data Collection Process**

| Data Collection Form       | Data Sources/Reporters  | Timing of Completion, if Prospectively Enrolled   | Data Collected   |
|----------------------------|---|---|--|
| Registration Form          | Identifiable: participant, obstetric HCP, and prescriber, if needed
Non-identifiable: HCP who enrolled participant | Enrollment  | 
 
• Registration information, including eligibility criteria
 
• Maternal demographic characteristics
 
• Maternal pre-pregnancy anthropometrics
 
• Maternal obstetrical history
 
• Family history of congenital malformations
 
• Disease information
 
• Baseline pregnancy information
 
• Maternal exposures during pregnancy
 
 |
| Pregnancy Information Form | Identifiable: obstetric HCP and prescriber, if needed
Non-identifiable: HCP who enrolled participant               | Enrollment, end of second trimester a , and EDD/pregnancy outcome a | 
 
• Ongoing pregnancy information
 
• Maternal exposures during pregnancy
 
   |
| Pregnancy Outcome Form     | Identifiable: obstetric HCP and pediatric HCP, if needed
Non-identifiable: HCP who enrolled participant            | EDD/pregnancy outcome   | Pregnancy outcome information  |

| Data Collection Form         | Data Sources/Reporters  | Timing of Completion, if Prospectively Enrolled       | Data Collected                                   |
|-------------------------------------|--|--|---|
| Maternal Lactation Information Form | Identifiable: participant, obstetric HCP, and pediatric HCP, if needed
Non-identifiable: HCP who enrolled participant | Enrollment, approximately 4 months and 1 year after delivery | Maternal lactation information                          |
| Infant Outcomes Form                | Identifiable: pediatric HCP
Non-identifiable: HCP who enrolled participant  | Approximately 4 months and 1 year after delivery             | Breastfeeding information
Infant outcome information |
| Targeted Follow-up Form             | Identifiable: obstetric, pediatric, or other HCP
Non-identifiable: HCP who enrolled participant                       | Any time after pregnancy outcome                             | Targeted follow-up information                          |

EDD = estimated date of delivery; HCP = healthcare provider; PV = pharmacovigilance.

a Obtain updated information since the previous contact.

### **6.1.1. Data Collected**

#### **6.1.1.1. Maternal Data**

##### ***Registration Information***

- Date of first contact with surveillance program
- Date of enrollment, defined as follows:
  - For participants who are self-enrolled and consented by the VRCC or participants who are enrolled and consented by their HCPs, date of enrollment is the date that informed consent is obtained
  - For participants who are enrolled under an IRB-/EC-approved waiver of informed consent and for whom only de-identified data are collected, date of enrollment is the date that the enrollment form is completed by the HCP
- Recruitment source(s)
- Minimum data for enrollment, including:
  - Pregnancy status
  - Omaveloxolone exposure information
  - Prior enrollment status

##### ***Maternal Demographic Characteristics***

- Year of birth
- Country of residence
- Occupation

- Ethnicity
- Race

***Maternal Pre-pregnancy Anthropometrics***

- Pre-pregnancy anthropometrics (weight and height)

***Maternal Obstetrical History***

- Number of previous pregnancies, including multiple gestations
- Outcomes of previous pregnancies (SAB, stillbirth, elective or therapeutic abortion, live birth)
- Characteristics of previous live births (preterm, SGA)
- Number of previous fetuses/infants with congenital malformations (major and minor) and contributing factors

***Family History of Congenital Malformations***

- Maternal and paternal family history of congenital malformations (major and minor), including specific malformation and relation of family member to mother or father

***Disease Information***

- Maternal history of FA, including date of diagnosis
- Characteristics of FA, including Friedreich's Ataxia Rating Scale scores

***Baseline Pregnancy Information***

- First day of last menstrual period (LMP)
- Method of conception

***Ongoing Pregnancy Information***

- Number of fetuses
- EDD and method of determination (i.e., LMP, ultrasound, or assisted reproductive technology [ART] data); if ultrasound-determined, timing of ultrasound (before 140/7, before 220/7, or at or after 220/7 gestational weeks)
- Prenatal tests performed, including name of test (e.g., ultrasound, amniocentesis, maternal serum alpha-fetoprotein, chorionic villus sampling), type of test (diagnostic or screening), date of test, and results/findings (e.g., congenital malformations)
- Concurrent maternal medical conditions, including:
  - Neurodegeneration
  - Cardiomyopathy
  - Thyroid abnormalities
  - Infectious diseases

- Asthma
- Diabetes
- Hypertension
- Seizure disorder
- Autoimmune diseases
- Depression and other psychiatric disorders
- Hepatitis
- Sexually transmitted diseases
- Uterine or cervical abnormalities, including congenital uterine abnormalities
- Concurrent pregnancy-related maternal medical conditions or pregnancy complications, including:
  - Pregnancy-induced hypertension
  - Pre-eclampsia
  - Eclampsia
  - Gestational diabetes
  - Preterm labor
  - Placental abruption
  - Ectopic pregnancy

***Maternal Exposures During Pregnancy***

- Exposure to omaveloxolone, including indication/reason for use, dose, route, frequency, and dates/duration of exposure, if available
- Exposure to other drugs or products (including prescription and non-prescription drugs, dietary supplements, vaccines, known teratogens, and investigational medications), including indication/reason for use, dose, route, frequency, and dates/duration of exposure, if available
- Exposure to tobacco, alcohol, marijuana, or recreational or illicit drugs, including timing of exposure, if available

***Pregnancy Outcome Information***

- Pregnancy outcome, classified in 1 of the following mutually exclusive categories: fetal loss (SAB, stillbirth, elective or therapeutic abortion, or fetal loss, type not specified) or live birth
- Date of pregnancy outcome
- Gestational age at pregnancy outcome
- Fetal/infant sex

- Fetal/infant weight, length, and head circumference at pregnancy outcome
- Route of delivery (i.e., spontaneous vaginal delivery, assisted vaginal delivery, or cesarean delivery)
- Congenital malformations (major and minor) and assessment of potential contributing factors
- For a noninduced fetal loss (SAB, stillbirth), factors that may have had an impact on the fetal loss and attribution (e.g., incompetent cervix, previous fetal loss)
- For elective or therapeutic abortion, reason (e.g., finding on prenatal test, risk to mother's health, undesired pregnancy)

***Maternal Lactation Information***

- Cracked or sore skin at site of lactation, insufficient production of milk, breast engorgement, mastitis

**6.1.1.2. Infant Data**

***Breastfeeding Information***

- Breastfeeding information, including breastfeeding start/stop dates and maternal medicinal and recreational exposures during breastfeeding

***Infant Outcome Information***

- Infant weight, length, and head circumference at birth (if not provided at pregnancy outcome) and at approximately 4 months and 1 year of age
- Achievement of the developmental milestones in each category as defined by the US Centers for Disease Control and Prevention (CDC) (social/emotional, language/communication, cognitive, and movement/physical development) at approximately 4 months and 1 year of age
- Congenital malformations (major and minor) and assessment of potential contributing factors
- Infant death, including date and cause of death
- Infant illnesses and hospitalizations

***Targeted Follow-up Information***

- Details of the congenital malformations (major or minor) or other condition of interest
- Etiology
- Outcome attribution
- Specific questions requested by the Sponsor and/or the birth defect evaluator

### **6.1.2. Attempts to Obtain Follow-up Information**

In the month that follow-up is due, the reporter will be contacted by the VRCC and asked to provide follow-up information. If needed, 3 subsequent attempts will be made approximately every 2 weeks via various modes of communication. If no response is received from the reporter, additional attempts may occur at the next planned data collection timepoint (e.g., at pregnancy outcome). When appropriate, the participant will be asked to encourage their HCP to provide the missing data. A final communication to obtain follow-up data will be sent via certified mail or an equivalent method indicating that the participant will be considered lost to follow-up if no further data are received. If, at any point in the follow-up process, the participant withdraws consent or the reporter indicates that the participant is lost to follow-up, no further attempts will be made. The reason the participant was lost to follow-up (e.g., no response from reporter, no response from participant, or participant withdrawal of consent) will be documented.

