### **7.3. Participants Lost to Follow-up**

A participant will be considered lost to follow-up if follow-up information is never obtained or is unavailable; pregnant individuals without pregnancy outcome information will be considered lost to follow-up, and live-born infants without follow-up data after birth will be considered lost to follow-up. See Section 6.1.2 for more information on the circumstances under which participants will be considered lost to follow-up. Participants who are lost to follow-up will be excluded from the analysis population, but their demographic and baseline characteristics will be summarized in the reports (see Section 9.2.1).

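### For consented participants, Section 6.1.2 ends all follow-up once one reporter says the participant is lost, although other sections collect contacts for that situation

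*Protocol*

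**What the plan says.** Section 6.1.2 sets an attempt schedule. The reporter is contacted in the month when follow-up is due, with three more attempts about two weeks apart if needed. Further tries may follow at the next planned timepoint, and a last letter goes by certified mail or similar. The section then adds an immediate stop that applies throughout: if "the participant withdraws consent or the reporter indicates that the participant is lost to follow-up, no further attempts will be made".

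Other sections bear on who can be asked:

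- Section 6.1 on reporters: "Enrolled individuals and the HCPs involved in their care or the care of their infants, if applicable, will serve as data reporters". It adds: "The surveillance program may also request data from other HCPs involved in the individual's or infant's care", once a medical release is in place.
- Section 4.1: a self-enrolling individual supplies "alternate contact information for a family member or friend outside of the household" and "contact information for HCPs who are/will be involved in their care or the care of their infants", with releases for those HCPs. HCPs who enroll with consent may also obtain releases.
- Section 5.2: the program will "attempt to collect contact information of family members or friends outside of the household in case the participant cannot be reached".
- Section 6.1 on waiver enrollees: the enrolling HCP supplies all follow-up.

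On the consequence, Section 7.3 states: "Participants who are lost to follow-up will be excluded from the analysis population". Loss there means no pregnancy outcome information or, for a live-born infant, no data after birth. Section 9.2.3 imputes nothing except the missing day in partial start and end dates. Section 9.1 anticipates about 10 to 20 enrollees.

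**The concern.** The stop rule joins two different events. Withdrawal of consent removes permission to contact anyone. A reporter's statement that the participant is lost shows only that this source has no information. A consented participant can have several sources: herself, an obstetric HCP, a pediatric HCP and a prescriber. A relative or friend may also help to locate her. Read literally, one HCP's statement closes the case before any of the others is tried.

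At stake are outcomes that could have been obtained. In a cohort this small, one outcome can decide whether an estimated prevalence is zero.

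**Working it through.** The plan states no loss rate, power or effect size. The 10 to 20 enrollees are a feasibility expectation, so there is no plan figure to reproduce. The check is a comparison of the text, followed by a sense of scale.

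**1. Stop rule against the contact provisions**

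| Situation | Section 6.1.2 | Other sections |
|---|---|---|
| Consent withdrawn | Stop at once | No conflict |
| Reporter silent | Three more attempts, possibly the next timepoint, final letter | No conflict |
| Reporter says lost, consented participant | Stop at once | Alternate contact (4.1, 5.2) and other HCPs (4.1, 6.1) could be tried |
| Reporter says lost, waiver enrollee | Stop at once | No other source (6.1), no conflict |

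The third row is the conflict. Section 5.2 wants the alternate contact "in case the participant cannot be reached, which can further promote retention", which is the very situation in which Section 6.1.2 stops. The rule is also uneven within its own section, since a silent reporter triggers more effort than one who replies. Table 1 lists only HCPs as identifiable sources for the pregnancy information, pregnancy outcome and infant forms, so the reporter who triggers the stop can easily be an HCP and not the participant.

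**2. From stop to exclusion**

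The statement itself deletes nothing. Exclusion follows only if outcome data are still missing, and data already received stay in. Under Sections 7.4 and 7.7, data from the participant alone would not bring her back in. Reaching her or a relative helps mainly by leading to an HCP who can report.

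**3. Scale**

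Share of enrollees per loss: 1/20 = 5% and 1/10 = 10%.

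One affected pregnancy kept or lost, with exact (Clopper-Pearson) 95% intervals. This assumes that every enrollee counts in the denominator; the real denominators will be smaller.

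| Enrolled | Kept | Lost |
|---|---|---|
| 10 | 1/10 = 10.0% (0.3 to 44.5) | 0/9 = 0% (0 to 33.6) |
| 20 | 1/20 = 5.0% (0.1 to 24.9) | 0/19 = 0% (0 to 17.6) |

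Chance of at least one such loss is 1 − (1 − t)^N, where t is an assumed probability that an enrollee is lost through this rule:

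| t | N = 10 | N = 20 |
|---|---|---|
| 5% | 40% | 64% |
| 10% | 65% | 88% |
| 20% | 89% | 99% |

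Bias: the full-cohort risk is (1 − t) × r0 + t × r1, where r0 is the risk in those retained and r1 the risk in those lost. The complete-case estimate targets r0. Assume t = 10% and r0 = 3%:

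| r1 | Full-cohort risk | Complete-case as share of full |
|---|---|---|
| 0% | 0.9 × 3% = 2.7% | 3/2.7 = 111% |
| 3% | 3.0% | 100% |
| 6% | 3.3% | 91% |
| 15% | 4.2% | 71% |
| 30% | 5.7% | 53% |

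The sign depends entirely on r1 relative to r0, and the protocol gives neither.

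**The case against.** The best defense is that Section 6.1.2 refers to the reporter, in the singular, and may be meant to govern only attempts to the person asked for the form then due. The section also lists non-response by the reporter and by the participant as separate reasons for loss. That reading is possible. But the sentence carries no such limit, and it attaches the same stop to withdrawal of consent, which must apply to everyone. A rule that staff can follow literally with this effect needs rewording.

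Three limits on the contacts are correct. The alternate contact is not a reporter. Section 4.1 describes collecting it at self-enrollment, and Section 5.2 promises only an attempt. Waiver enrollees have a single source, so stopping on that HCP's word is sensible.

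A reader might infer that the rule selectively drops pregnancies transferred to another center because of complications, and so biases prevalence downward. The documents do not support this. They never mention transfer of care, a known transfer is not the same as a loss, and nothing shows worse outcomes among those lost. Adverse outcomes also have a second route to the coordination center, because Sections 12.1.2 and 12.3.2 make fetal losses, malformations, and preterm and small births reportable as serious adverse events. That route still needs an HCP who knows the outcome and reports it.

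A reader might also take a postnatal loss as removing the infant from the malformation analysis. That is not clear. Section 7.7 and Table 3 ask only for pregnancy outcome data, whereas Section 7.3 words infant loss more broadly.

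Finally, Section 9.2.4 admits that lost cases may differ and plans to compare characteristics descriptively. This is fair disclosure, but it recovers no outcomes.

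**Conclusion.** The point holds for consented participants. As written, the stop rule conflicts with the retention provisions and can produce avoidable missing outcomes. Each such loss is 5% to 10% of the anticipated enrollment, and a larger share of any analysis with a smaller denominator. How often it would happen is unknown; the probabilities above rest on assumed loss rates. Bias arises only if lost and retained cases differ in risk, and its direction and size cannot be derived from the documents. The correction is worth making because it is cheap and the cohort is very small, and it needs no claim of demonstrated bias.

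**What to change.** In Section 6.1.2, make withdrawal of consent the only immediate stop. Then add wording along these lines: for a consented participant, when one reporter indicates loss to follow-up, the coordination center will try the participant, any alternate contact held, and the other HCPs covered by a medical release, on the existing attempt schedule, before she is classed as lost. Where an HCP now involved has no release, seek one through the participant. Leave the rule unchanged for waiver enrollees.

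The cost is a protocol wording change and a few extra contacts per affected participant, with an occasional new release. No visits, tests or analyses are added.
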